11.1. Adverse Event Management

Adverse events (AE), which include clinical laboratory test variables, will be monitored and documented from the time of informed consent. Subjects should be instructed to report any AE that they experience to the investigator. Investigators should make an assessment for AEs at each visit and record the event on the appropriate eCRF.

Wherever possible, a specific disease or syndrome rather than individual associated signs and symptoms should be identified by the investigator and recorded on the eCRF. However, if an observed or reported sign or symptom is not considered a component of a specific disease or syndrome by the investigator, it should be recorded as a separate adverse event on the eCRF. Additionally, the condition that led to a medical or surgical procedure (e.g., surgery, endoscopy, tooth extraction, or transfusion) should be recorded as an AE, not the procedure.

Any medical condition already present at Screening should not be reported as an AE unless the medical condition or signs or symptoms present at Screening change in severity or seriousness at any time during the study. In this case, it should be reported as an AE.

Clinically significant abnormal laboratory or other examination (e.g., electrocardiogram) findings that are detected during the study or are present at Screening and significantly worsen during the study should be assessed for an AE. The investigator will exercise their medical and scientific judgment in deciding whether an abnormal laboratory finding or other abnormal assessment is clinically significant. Clinically significant abnormal laboratory values occurring during the clinical study will be followed until repeat tests return to normal, stabilize, or are no longer clinically significant. Any abnormal test that is determined to be an error does not require reporting as an AE.

For all CDI recurrences, information is recorded on the Follow-up eCRF and applicable CDI eCRF. Recurrence of CDI is not to be reported as an AE unless hospitalization \geq 24 hours is required as part of treatment. If hospitalization \geq 24 hours is required, the event qualifies as an AE and is to be reported as an SAE (see **Section 11.14** for sponsor reporting requirements).

AEs should be followed until the event resolves or the subject exits the study. Chronic condition is defined as a condition lasting > 3 months.

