6.6. Safety Endpoints

1. Number of adverse events per subject

2. Timing of attributable TEAEs
3. Duration of TEAEs
4. Relatedness of TEAEs
5. Severity of TEAEs
6. Causality of TEAEs to IP, enema, *C. difficile* or prior condition
7. Number of each of the following CDI-related TEAEs through 8-weeks post treatment: death, septic shock, toxic megacolon, colonic perforation, emergency colectomy, and ICU admission
8. Onset of new chronic conditions relative to treatment administration

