11.2. AE Definitions

- Adverse event: an adverse event (AE) is any untoward medical occurrence in a clinical investigation subject associated with the use of IP, which does not necessarily have a causal relationship with the treatment. An AE can therefore be any unfavorable and/or unintended sign (including an abnormal laboratory finding), symptom, or disease temporally associated with the use of IP.
 - All AEs, including observed or volunteered problems, complaints, or symptoms are to be recorded on the eCRF within **ten (10) business days** of site awareness.
- Adverse reaction: All noxious and unintended responses to IP should be considered an adverse reaction. “Responses” to IP means that a causal relationship between IP and an AE is at least a reasonable possibility, i.e., the relationship cannot be ruled out.
- Serious adverse event (SAE): An AE or adverse reaction is considered serious if, in the view of either the investigator, Medical Monitor or sponsor, it results in any of the following outcomes:
 - Death
 - Life-threatening adverse event

NOTE: An adverse event or adverse reaction is considered “life-threatening” if, in view of either the investigator or Sponsor, its occurrence places the subject at immediate risk of death. It does not include an event that, had it occurred in a more severe form, might have caused death.

- Hospitalization \geq 24 hours or prolongation of an existing hospitalization

NOTE: Any hospital admission with at least one overnight stay will be considered an inpatient hospitalization. An emergency room visit without hospital admission will not be recorded as a serious adverse event (SAE) under this criterion, nor will hospitalization for a procedure scheduled or planned before signing of informed consent. However, unexpected complications and/or prolongation of hospitalization that occur during elective surgery should be recorded as AEs and assessed for seriousness. Admission to the hospital for social or situational reasons (i.e., no place to stay, live

too far away to come for hospital visits) will not be considered inpatient hospitalizations.

- Persistent or significant incapacity or substantial disruption of the ability to conduct normal life functions.
- Congenital anomaly/birth defect.
- Important medical event

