11.13. Study Stopping Rules for Safety

Rebiotix will oversee review of all AEs reported during the study to observe for trends and unanticipated events, either in severity, seriousness or incidence, and to assess if a study stopping rule may be triggered. AE review includes the event description, onset date in relation to the treatment date, and the investigator's determination of causal relatedness to IP, the enema procedure, and pre-existing condition, as well as rating the event's severity and seriousness. Additionally, the Medical Monitor assessment of seriousness and causality will be provided and reviewed as it may be different from the site investigator report of the event. Anticipated AEs may trigger the study stopping rules.

The DSMB will determine whether enrollment should be paused, the study terminated, or other actions taken based on their assessment that:

- a) There is probable cause that IP or enema procedure (e.g., due to transfer from an RBX2660 donor) contributed to a pathogenic intestinal infection in the stool of any subject, or
- b) Any events of major significance such as death or other serious outcome for which a causal connection with the IP is plausible and represents an excess of the important adverse event(s).

To support the DSMB assessment, the Rebiotix Operations Department may be asked to review the donor history and batch processing/release records for the product unit(s) administered in these cases, and forward its report to the DSMB Chair for review. The DSMB Chair will review the Operations Department report. If probable cause is suspected, the DSMB Chair will convene the entire DSMB for event review.

Upon the DSMB's determination of action, the Chair will notify Rebiotix, who will notify the study sites.

If enrollment is stopped, Rebiotix and the study sites will assess for the occurrence of similar events, and evaluate IP and study records for possible root cause(s). Enrollment may be re-started upon further review and approval from the DSMB. As appropriate, the DSMB may recommend study termination or measures short of termination with the objective of reducing the risk of AEs.

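### The AE exemption for CDI recurrence has one exit, a required hospital stay, so a recurrence that is serious on other grounds is not routed to SAE reporting

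*Protocol*

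**What the plan says.** Protocol 11.1 sends every recurrence to dedicated forms: "For all CDI recurrences, information is recorded on the Follow-up eCRF and applicable CDI eCRF". It then sets the exemption: "Recurrence of CDI is not to be reported as an AE unless hospitalization" of at least 24 hours is required as part of treatment. When that condition is met, "the event qualifies as an AE and is to be reported as an SAE". No other exception is written.

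Protocol 11.2 defines seriousness: "An AE or adverse reaction is considered serious if, in the view of either the investigator, Medical Monitor or sponsor", one of several outcomes follows. Hospitalization of at least 24 hours is one of these. The others are death, a life-threatening event, prolongation of an existing stay, incapacity, congenital anomaly and important medical event.

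Protocol 6.6, item 7 defines a safety endpoint that begins "Number of each of the following CDI-related TEAEs through 8-weeks post treatment: death, septic shock, toxic megacolon" and continues with colonic perforation, emergency colectomy and ICU admission. SAP 5.4.2 repeats it. SAP 5.4.4.2 and 6.6.2.2 collect and summarize the same six outcomes through the 6-month call after the last enema, and do not make this depend on AE status.

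For the stopping rules, Protocol 11.13 says: "Rebiotix will oversee review of all AEs reported during the study".

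**The concern.** Keeping an adjudicated efficacy event out of routine AE reporting is a reasonable design choice. The difficulty is that the exception for serious cases uses one seriousness criterion where the protocol's own definition has several. A recurrence can be fatal or life-threatening, or can prolong a stay begun for another reason, without a new stay of at least 24 hours being required to treat it.

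Safety is the primary objective, and the population is meant to be broader than in earlier studies. Serious C. difficile-related events do occur in this program: 16 of 54 serious TEAEs in study 2017-01 were related to C. difficile (Protocol 5.3.4). In study 2015-01 one death was reported as definitely related to C. difficile and possibly related to product or procedure (Protocol 5.3.3), although the text does not say whether a hospital stay was involved. Any omission works in one direction: it can lower the counts of serious and fatal TEAEs but cannot raise them.

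**Working it through.** The plan gives no figure to reproduce: 750 is a treatment cap, and SAP 3.3 says there is no powering. The check follows a confirmed recurrence that is serious for a reason other than a required stay of at least 24 hours.

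| Step | Rule | Result for this recurrence |
|---|---|---|
| AE status (Protocol 11.1) | AE only if a stay of at least 24 hours is required | Not an AE |
| SAE status (Protocol 11.2) | Criteria apply to an AE or adverse reaction | Not an SAE, whatever the outcome |
| 24-hour report (Protocol 11.6.1) | Any AE meeting a serious criterion | Not triggered |
| Medical Monitor (Protocol 7.6, 11.10) | SAEs, and events reported as related to product or procedure | Not reached as an SAE |
| TEAE tables (SAP 5.4.3.4, 6.6.2.1) | TEAEs derived from AEs by onset date | Absent from all-TEAE, serious-TEAE and fatal-TEAE tables |
| Stopping-rule surveillance (Protocol 11.13) | Starts from reported AEs | Not in the reviewed stream |
| Complication summary (SAP 5.4.4.2, 6.6.2.2) | Six outcomes, no AE condition | Included if one of the six occurred |

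The last row leaves two gaps for endpoint 7.

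1. **Source.** The endpoint counts TEAEs, while the SAP summary counts collected complications. Nothing says which feeds the endpoint. The data listed for a possible-recurrence visit (Protocol 10.13) name no complication. Death appears as an exit reason (Protocol 10.15), and ICU admission in the hospitalization details (SAP 5.4.4.3).
2. **Window.** The endpoint runs through 8 weeks; SAP 6.6.2.2 runs through 6 months after the last enema.

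For scale only, take non-success at 8 weeks in earlier studies as recurrence:

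- Study 2019-02 (Protocol 5.3.5): 750 × (1 − 0.828) = 129.
- Study 2017-01 (Protocol 5.3.4): 750 × (1 − 0.704) = 222.

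These counts include recurrences that are hospitalized and so leave the exemption. Let q be the share that is serious without the required stay. The documents give no value for q, so the values below are assumptions.

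| Assumed q | 129 × q | 222 × q |
|---|---|---|
| 0.1% | 0.13 | 0.22 |
| 1% | 1.3 | 2.2 |
| 5% | 6.5 | 11.1 |

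The result runs from well under one event to 11, depending entirely on q. This is not an estimate.

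**The case against.** The best defense is that the exemption covers recurrence and nothing else. On-study recurrence is defined by loose stools plus a positive central-laboratory test (Protocol 7.3.4.2). Septic shock or perforation is a different event. Table 11-1 grades shock, toxic megacolon and perforation as AE severities, and Section 11.8 encourages an investigator who is unsure to enter the finding as an AE. This stands in part: distinct complications are not expressly exempt. But Section 11.1 also says that "a specific disease or syndrome rather than individual associated signs and symptoms should be identified by the investigator", which pulls the complication back toward the exempt diagnosis. The text does not settle the matter.

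Two further points narrow the gap. A death before central-laboratory confirmation does not meet the definition of recurrence, so the exemption does not reach it. And the stay must be required, not completed, so a subject admitted for such treatment who dies within hours can still qualify.

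It can also be argued that recurrent CDI is the entry condition, and that Sections 11.1 and 11.5 make a worsening pre-existing condition reportable. That general rule does not clearly override the specific sentence on recurrence.

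The stopping criterion in Section 11.13 speaks of events of major significance, not only AEs, and the DSMB may review efficacy outcomes (Protocol 11.11). Both are true, but the surveillance that brings cases forward is described as a review of AEs.

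A reader might infer that every serious recurrence drops out of endpoint 7. The documents do not support that. The endpoint covers six named outcomes, so a recurrence serious in some other way was never in it, and the SAP collects all six without requiring AE status.

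**Conclusion.** The concern holds as a reporting-route defect. Followed as written, Protocol 11.1 keeps a confirmed recurrence that is serious without a required stay of at least 24 hours out of SAE reporting, the Medical Monitor's SAE review, the TEAE tables and AE-based safety surveillance. This conflicts with the evident purpose of Section 11.2. For endpoint 7 the finding is narrower: its source is unstated and its window differs from that of the matching SAP summary.

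The size cannot be estimated. It is probably small, on the assumption that most such recurrences would need a qualifying stay. A reader might apply a rate to 222 recurrences and conclude that a specific number of serious events is lost. That is not supported: no document gives the rate, the 222 includes hospitalized failures, and the separate collection means that events need not be lost. The primary endpoint, which counts TEAEs related to product or enema, is little affected if these recurrences are attributed to C. difficile rather than to treatment. The case for change rests on oversight: a single CDI death that bypasses 24-hour reporting matters in a safety study.

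**What to change.** **Protocol 11.1.** Reconcile the exemption with Sections 11.2 and 11.6.1. Suggested wording: *A CDI recurrence is reported as an AE only if it meets any serious criterion in Section 11.2 or involves a complication listed in Section 6.6, item 7; such an event is reported as an SAE.* The present hospitalization exit is kept, since it is one of the Section 11.2 criteria. In the same edit, reconcile the 24-hour test with the Section 11.2 note that counts any admission with an overnight stay.

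**SAP 6.6.2.2.** State that endpoint 7 is counted from these SAEs together with the CDI eCRF and study-exit death records, that each subject-event is counted once, and that onset is through 8 weeks. Report the 6-month complication summary separately.

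The cost is one protocol sentence, a short SAP addition and a few more SAE reports. Routine recurrences stay exempt, and the efficacy definitions do not change.

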11.2. AE Definitions

- Adverse event: an adverse event (AE) is any untoward medical occurrence in a clinical investigation subject associated with the use of IP, which does not necessarily have a causal relationship with the treatment. An AE can therefore be any unfavorable and/or unintended sign (including an abnormal laboratory finding), symptom, or disease temporally associated with the use of IP.
 - All AEs, including observed or volunteered problems, complaints, or symptoms are to be recorded on the eCRF within **ten (10) business days** of site awareness.
- Adverse reaction: All noxious and unintended responses to IP should be considered an adverse reaction. “Responses” to IP means that a causal relationship between IP and an AE is at least a reasonable possibility, i.e., the relationship cannot be ruled out.
- Serious adverse event (SAE): An AE or adverse reaction is considered serious if, in the view of either the investigator, Medical Monitor or sponsor, it results in any of the following outcomes:
 - Death
 - Life-threatening adverse event

NOTE: An adverse event or adverse reaction is considered “life-threatening” if, in view of either the investigator or Sponsor, its occurrence places the subject at immediate risk of death. It does not include an event that, had it occurred in a more severe form, might have caused death.

- Hospitalization \geq 24 hours or prolongation of an existing hospitalization

NOTE: Any hospital admission with at least one overnight stay will be considered an inpatient hospitalization. An emergency room visit without hospital admission will not be recorded as a serious adverse event (SAE) under this criterion, nor will hospitalization for a procedure scheduled or planned before signing of informed consent. However, unexpected complications and/or prolongation of hospitalization that occur during elective surgery should be recorded as AEs and assessed for seriousness. Admission to the hospital for social or situational reasons (i.e., no place to stay, live

too far away to come for hospital visits) will not be considered inpatient hospitalizations.

- Persistent or significant incapacity or substantial disruption of the ability to conduct normal life functions.
- Congenital anomaly/birth defect.
- Important medical event

NOTE: Important medical events that may not result in death, be life-threatening, or do require hospitalization may be considered serious when, based upon appropriate medical judgment, they may jeopardize the subject and may require medical or surgical intervention to prevent one of the outcomes above. Examples of such medical events include allergic bronchospasm requiring intensive treatment in an emergency room or at home, blood dyscrasias or convulsions that do not result in inpatient hospitalizations, or the development of drug dependency.

- Unexpected Adverse Reaction: An adverse reaction, the nature or severity of which is not consistent with the applicable product information.
- Unexpected adverse event or unexpected suspected adverse reaction: An AE or suspected adverse reaction is considered “unexpected” if it is not listed in the Investigator’s Brochure or is not listed at the specificity or severity that has been observed.

11.3. Anticipated Adverse Events

The following is list of anticipated AEs that may or may not be causally related to IP, the enema procedure, or CDI:

- gas (flatulence)
- belching
- abdominal distension or bloating
- increased diarrhea
- abdominal cramping or pain
- constipation
- colitis
- fever $\geq 37.8^{\circ}$ C (100.0°F)
- fatigue
- chills

- transmission of disease from the donor to recipient
- rectal irritation or pain
- rectal bleeding
- nausea
- vomiting
- hypotension
- puncture of the intestine

11.4. Solicited Events

The following list of anticipated events are solicited from subjects via the Subject Diary:

- gas (flatulence)
- abdominal distension or bloating
- rectal irritation or pain
- chills/severe shivering
- abdominal pain or cramping
- increased diarrhea
- constipation
- rectal bleeding
- nausea
- vomiting
- fever $\geq 37.8^{\circ}$ C (100.0° F)

Through the completion of the Subject Diary, subjects are asked specific questions regarding frequency and severity of the solicited AEs.

11.5. Preexisting Condition

A preexisting condition, including abnormal physical exam findings, is one that is present at the start of the study and is to be recorded at the time of the Screening visit. A preexisting condition is only to be recorded as an adverse event if the frequency, intensity or the character of the condition worsens during study participation.

11.6. Serious Adverse Event Reporting – Procedures for Investigators

11.6.1. Initial Reports

All SAEs occurring from the time of informed consent until 6 months after administration of the last study enema of IP must be reported to Medpace Clinical Safety **within 24 hours** of the knowledge of the occurrence (this refers to any AE that meets any of the aforementioned serious criteria).

To report the SAE, complete the SAE form electronically in the electronic data capture (EDC) system for the study. When the form is completed, Medpace Safety personnel will be notified electronically and will retrieve the form. If the event meets serious criteria and it is not possible to access the EDC system, send an email to Medpace Safety at [contact] or call the Medpace SAE hotline (phone number listed below), and fax the completed paper SAE form to Medpace (fax number listed below) within 24 hours of awareness. When the EDC system becomes available, the SAE information must be entered within 24 hours of the system becoming available.

Safety Contact Information:
Medpace Clinical Safety

Medpace SAE hotline:

[REDACTED]

11.6.2. Follow-Up Reports

The investigator must continue to follow the subject until the SAE has subsided or until the condition becomes chronic in nature, stabilizes (in the case of persistent impairment) or the subject dies. Chronic is defined as a condition lasting >3 months.

Within 24 hours of receipt of follow-up information, the investigator must update the SAE form electronically in the EDC system for the study and submit any supporting documentation (e.g., subject discharge summary or autopsy reports) to Medpace Clinical Safety via fax or e-mail. If it is not possible to access the EDC system, refer to the procedures outlined above for initial reporting of SAEs.

11.7. Grading Event Severity

Identified, subject-reported and unsolicited AEs are to be graded, according to severity, by the site investigator. For this classification of events, severity is not the same as

seriousness, which is defined in **Section 11.1**. Severity is an indication of the *intensity* of a specific event (e.g., mild, moderate or severe). Classification of an event as serious relates to an event's outcome or intervention criteria and is usually associated with events that pose a threat to a subject's life or functioning. An event can be severe but not serious, such as a migraine.

Using the definitions in **Table 11-1**, the site investigator will categorize the severity of a solicited or unsolicited event on the AE eCRF. If a particular event is not listed on this table, the NIH/NCI Common Terminology Criteria for Adverse Events found at online at the following address may be utilized.

https://ctep.cancer.gov/protocolDevelopment/electronic_applications/docs/CTCAE_v5_Quick_Reference_8.5x11.pdf

Table 11-1: Severity Grading Table*

Parameter	Grade 1: Mild	Grade 2: Moderate	Grade 3: Severe	Grade 4: Potentially Life-threatening
Flatulence (gas)	Symptoms causing no or minimal interference with usual social and functional activities	Symptoms causing greater than minimal interference with usual social and functional activities	NA	NA
Belching (burping)	Symptoms causing no or minimal interference with usual social and functional activities	Symptoms causing greater than minimal interference with usual social and functional activities	NA	NA
Abdominal distension or bloating	Symptoms causing no or minimal interference with usual social and functional activities	Symptoms causing greater than minimal interference with usual social and functional activities	Symptoms causing inability to perform usual social and functional activities	NA
Increased diarrhea	Increase of ≤ 3 stools over baseline per 24-hour period	Increase of 4 – 6 stools over baseline per 24-hour period	Bloody diarrhea if not present at baseline OR increase of ≥ 7 stools over baseline per 24-hour period OR IV fluid replacement indicated if not indicated at baseline	Life-threatening consequences, e.g., hypotensive shock

Parameter	Grade 1: Mild	Grade 2: Moderate	Grade 3: Severe	Grade 4: Potentially Life-threatening
Abdominal cramping/pain	Discomfort/pain causing no or minimal interference with usual social and functional activities	Discomfort/pain causing greater than minimal interference with usual social and functional activities	Discomfort/pain causing inability to perform usual social and functional activities	Disabling pain causing inability to perform basic self-care OR inpatient hospitalization \geq 24 hours
Constipation	Occasional or intermittent symptoms, occasional use of stool softeners, laxatives, dietary modifications or enema	Persistent symptoms with regular use of laxatives or enemas indicated	Symptoms causing inability to perform usual social and/or functional activities	Life-threatening consequences, e.g., obstruction, toxic megacolon
Colitis	No symptoms, regardless of pathologic or radiographic evidence of inflammation	Abdominal pain, mucus or blood in the stool	Abdominal pain, fever, change in bowel habits with ileus; peritoneal signs	Life-threatening consequences, e.g., perforation, bleeding, ischemia, necrosis, toxic megacolon
Fever	37.8 – 38.6°C (100.0 – 101.5° F)	38.7 – 39.3°C (101.6 – 102.8° F)	39.4 – 40.5°C (102.9 – 104.9° F)	> 40.5°C (104.9° F)
Fatigue/ malaise	Symptoms causing no or minimal interference with usual social and functional activities	Symptoms causing greater than minimal interference with usual social and functional activities	Symptoms causing inability to perform usual social and functional activities	Incapacitating fatigue/malaise symptoms causing inability to perform basic self-care functions
Chills	Symptoms causing no or minimal interference with usual social and functional activities	Symptoms causing greater than minimal interference with usual social and functional activities	Symptoms causing inability to perform usual social and functional activities	NA
Rectal discomfort or irritation	No symptoms or symptoms not requiring medical intervention	Symptomatic with medical intervention (topical medications / treatments) indicated	Symptoms causing inability to perform usual social and functional activities or requiring medical intervention other than topical medications / treatments	NA

Parameter	Grade 1: Mild	Grade 2: Moderate	Grade 3: Severe	Grade 4: Potentially Life-threatening
Rectal bleeding	Mild or intermittent without transfusion	Persistent without transfusion	Requires transfusion	Life-threatening consequences
Nausea	Transient (\leq 24 hours) or intermittent nausea with no or minimal interference with oral intake	Persistent nausea resulting in decreased intake for 24-48 hours	Persistent nausea resulting in decreased intake $>$ 48 hours OR aggressive rehydration indicated, e.g., IV fluids	Life-threatening consequence, e.g., hypotensive shock
Vomiting	Transient (\leq 24 hours) or intermittent vomiting with no or minimal interference with oral intake	Frequent episodes of vomiting with no or mild dehydration	Persistent vomiting resulting in orthostatic hypotension OR aggressive rehydration indicated, e.g., IV fluids	Life-threatening consequence, e.g., hypotensive shock
Hypotension	NA	Symptomatic, corrected with oral fluid replacement	Symptomatic, IV fluids indicated	Shock requiring use of vasopressors or mechanical assistance to maintain blood pressure
Adverse event not identified elsewhere in this table	Symptoms causing no or minimal interference with usual social and functional activities	Symptoms causing greater than minimal interference with usual social and functional activities	Symptoms causing inability to perform usual social and functional activities	Symptoms causing inability to perform basic self-care functions OR medical or operative intervention indicated to prevent permanent impairment, persistent disability, or death

*Adapted from Division of AIDS Table for Grading of Severity of Adult and Pediatric Adverse Events and Addendum 3: Rectal Grading Table for Use in Microbicide Studies; May 2012.

